6. BENEFITS

Subjects may experience the benefit of better health behavior and the Timpany Center may have improved ability to address the diabetes epidemic

7. PRIVACY AND CONFIDENTIALITY

All participant information and specimens are handled in compliance with the Health Insurance Portability and Accountability Act (HIPAA) and privacy policies of Stanford University, Stanford Health Care, and Stanford Children's Health.

A Patient-Centered Strategy for Improving Diabetes Prevention in Urban American Indians

02266576

Statistical Analysis Plan

October 9, 2019

CHANGES FROM ORIGINAL PROTOCOL

1. The second investigational site was changed from Indian Health Center of Santa Clara Valley to the Timpany Center at the San Jose State University Research Foundation.
2. Blood samples were obtained by fingerstick method rather blood draw.

METHODS

The primary model for participant j at time k nested in cohort i

$$\begin{aligned} \text{Outcome}_{ijk} = & \beta_0 + \beta_{0i} \\ & + \beta_{0ij} + \beta_1 \text{Intervention}_j + \beta_2 \text{Month6}_{jk} + \beta_3 \text{Month12}_{jk} + \beta_4 \text{Month18}_{jk} \\ & + \beta_5 \text{Intervention}_j * \text{Month6}_{jk} + \beta_6 \text{Intervention}_j \\ & * \text{Month12}_{jk} + \beta_7 \text{Intervention}_j * \text{Month18}_{jk} + \beta_8 \text{Gender}_j + \varepsilon_{ijk} \end{aligned}$$

will be used to test the co-primary hypotheses that BMI will decrease and quality of life will increase in the enhanced DPP arm relative to the standard DPP arm upon completion of the study. The linear regression model includes a random intercept β_{0i} to account for within cohort correlation, a random intercept β_{0ij} to account for within participant correlation, and adjusts for gender (Gender_j), the stratification factor for randomization. Intervention_j indicates that participant j is in the enhanced DPP arm and Month6_{jk} , Month12_{jk} , and Month18_{jk} indicate whether observation k from subject j is at month 6, 12, or 18, respectively. To test whether the change in the primary outcome from baseline at 12 months differs between the standard and enhanced arms, we will test the null hypothesis that $\beta_6 = 0$ using the Wald test. Each outcome will be tested at a two-sided $\alpha = 0.05$ for an overall $\alpha = 0.10$.

The primary analyses will follow the intent-to-treat principle and will use all available data. We will describe any missing data and will conduct sensitivity analyses to evaluate the impact of the missing data on our conclusions. Sensitivity analyses considered to evaluate the robustness of our findings to the presence of missing data will include multiple imputation methods and worst-case imputation where missing values are filled with an extreme value (eg 5% greater than value observed at baseline), which can be used to determine how extreme the unobserved missing values would need to be in order to change the conclusion of the trial.^{51,52} Secondary analyses will replace the primary outcome in the model above with secondary outcomes.

Additional secondary analyses will consider pre-specified moderators and mediators (depressive symptoms, coping skills, and social support/community cohesion) of the primary outcomes. We will investigate the moderators and mediators using mixed effects linear regression by including an interaction term of treatment and the hypothesized moderator and centering the independent variables.^{53,54}

SAMPLE SIZE AND DATA INTERPRETATION

Our study was designed to provide sufficient statistical power to test the study's co-primary hypothesis that the enhanced DPP will result in greater weight loss and quality of life improvement compared to the standard DPP. In determining the sample size we considered the definition of clinically significant weight loss, the standard deviation of weight change in past clinical trials of lifestyle interventions, and acceptable levels of Type I and Type II errors. Our power estimates are based on simplified assumptions and the actual power may be different because of the correlated errors induced by the cohort effect and the repeated measures over time. In the original DPP trial, the average weight loss in the intensive intervention arm was $6.9\% \pm 4.5\%$ after 6 months of follow up and $4.9\% \pm 7.4\%$ at the end of the trial (mean follow-up of 3.2 years).⁵⁵ This percent weight loss is similar to other studies and greater than that observed in the SDPI evaluation where Jiang et al reported a percent weight loss of 4.4% following the 16-week program.¹⁰ Based on this literature, we expect a mean percent weight loss of 4.0% in the standard DPP and 6.5% in the enhanced DPP. To be conservative, we powered the study to be able to detect a difference of 2.0%. Dividing a 2.0% difference (6.0%-4.0%) by the DPP SD (4.5%) yields an effect size of approximately 0.45. A sample of 81 participants per arm will be required to compare the standard and enhanced arms for an effect size of 0.45 at a two-sided $\alpha=0.05$ with 80% power. We estimate 20% will be missing BMI at follow-up and have therefore inflated the initial sample size to 102 participants per arm. As the secondary analyses are exploratory, no adjustment for multiple testing will be made for secondary analyses. The secondary analyses are not intended to produce clinically actionable results, but rather to supplement conclusions based on the primary analysis and to inform future research. They will be interpreted properly within that context, considering the totality of evidence available.

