Participants will be recruited by Timpany Center staff and community members. If they are otherwise eligible except that some of their information is more than 3 months old, we will conduct a clinical screening to collect recent blood pressure, and blood test for cholesterol and blood sugar. They will consent in- person for the clinical screening. Eligible participants will receive an explanation about the study and sign the full study consent form. After signing the consent form, the participant completes baseline data collection. This includes an interviewer administered questionnaire, a blood test, clinical measurements, and wearing a pedometer for 7 days. After all baseline data is collected, the participant is randomly assigned to ONE of two groups: 1) diabetes prevention program (DPP) or 2) enhanced diabetes prevention program (DPP+).

There are 102 people in the standard DPP and 102 people in the enhanced diabetes prevention program to address historical trauma (DPP+). Participants will complete 3 evaluations during the research study: baseline, 5 months (1 week following the conclusion of intervention). Participants enrolled in the last cohorts will not have as many follow-up evaluations as those enrolled in initial cohorts. The evaluations include blood draws, other measurements (blood pressure, height, weight, and waist circumference), and a series of questionnaires. Blood samples and other measurements will be collected at all of the evaluation visits (baseline, 5 months, 8 months, 14 months, and 20 months) after a more than 8 hour fast. The volume of most blood samples will be 20 cc's (approximately 1.5 tablespoons). Any samples left over after analysis will be destroyed when the study is completed. Questionnaires include a series of questions about their eating patterns, physical activity habits, smoking status, past medical history, current medications, use of additional health care resources, resilience, and emotional status. Questionnaires will be filled out at the clinic visits at baseline, 5 months, 8 months, 14 months, and 20 months.

b. Procedure Risks

We have designed this study to be least risky through the following means:

- 1) The intervention targets improvement of behaviors (diet, exercise, stress reduction) that can help decrease weight; thereby, decreasing the chance of cardiovascular disease.
- 2) The intervention recommendations are based on accepted clinical guidelines.

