- 3) The intervention builds on previous trials conducted by key investigators on this project.

c. Use of Deception in the Study:

Deception will not be used in the research study.

d. Use of Audio and Video Recordings

We may use audio recording or video recording for Talking Circles, Modified Photovoice, Digital Storytelling, CAB meetings, and intervention classes for research purposes to analyze transcribed data and for educational purposes in order to review how the health educators are presenting the protocol to the participants. We may also use audio recording for interviewing participants about how they feel about the health education they receive.

We will also use camera pictures (and accompanying written or audio narrative) and video footage created by participants to share cultural stories, and perceptions of health needs and assets in the AIAN community. Audio recordings from interview debriefings will be destroyed once they have been transcribed. Photos, videos, and accompanying audio from Modified Photo Voice and Digital Storytelling maybe used for educational purposes, such as during community presentations or scientific meetings and

conferences. Photos, videos, and audio will not be linked to individuals unless we have received express written approval to use the media for a given purpose.

e. Alternative Procedures or Courses of Treatment

Standard treatments for weight management and diabetes prevention will be described to all participants. This program utilizes existing standards of care. No standard treatment is being withheld. The alternative is not to participate and to individually pursue an exercise program(s), work with a personal trainer, or consult with a dietitian on diet modifications.

f. Will it be possible to continue the more (most) appropriate therapy for the participant(s) after the conclusion of the study?

If funding allows, we will continue with the enhanced diabetes prevention program. However, the enhanced components of the program may not typically be covered by the Indian Health Center of Santa Clara Valley, so we do not guarantee it.

g. Study Endpoint(s)

Because our primary end point is increased resilience and weight loss for diabetes prevention, we do not expect any adverse events to cause us to terminate the study early. We plan to continue the study for the full 20 months and provide participants with the opportunity to participate in several follow-up focus groups to contextualize study results.

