- iv. Inappropriate for moderate exercise according to the Revised Physical Activity Readiness Questionnaire;
- v. Pregnant, planning to become pregnant, or lactating;
- vi. Family household member already enrolled in the study;
- vii. Already enrolled or planning to enroll in a clinical trial that would limit full participation in the

study;

- viii. Resident of a long- term care facility;
- ix. Lack of spoken English by patient or a household member > 18 y who can serve as interpreter;
- x. Plans to move during the study period (9 months post-randomization);
- xi. Investigator discretion for clinical safety or adherence reasons (e.g., unstable housing, chronic pain).

i. Screening Procedures

Exclusion criteria for Randomized Controlled Trial

- i. Significant medical comorbidities, including uncontrolled metabolic disorders (e.g., thyroid, diabetes, renal, liver), unstable heart disease, heart failure, and ongoing substance abuse;
- ii. On greater than 10 prescription medications;
- iii. Psychiatric disorders requiring atypical antipsychotics or multiple medications;
- iv. Inappropriate for moderate exercise according to the Revised Physical Activity Readiness Questionnaire;
- v. Pregnant, planning to become pregnant, or lactating;
- vi. Family household member already enrolled in the study;
- vii. Already enrolled or planning to enroll in a clinical trial that would limit full participation in the study;
- viii. Resident of a long-term care facility;
- ix. Lack of spoken English by patient or a household member > 18 y who can serve as interpreter;
- x. Plans to move during the study period (9 months post-randomization);
- xi. Investigator discretion for clinical safety or adherence reasons (e.g., unstable housing, chronic pain).

j. Participation in Multiple Protocols

Participants will be asked about participation in other studies during the screening process. If they are in another study, they will need to gain approval from both study protocol directors to remain in both studies. Additionally, they will be asked to inform study researchers if they join another study during the duration of their participation in this study.

k. Payments to Participants

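### The co-primary hypotheses are worded for the end of the study, but the only stated primary test is the arm contrast at 12 months, which is neither the last time in the model nor a protocol visit

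*SAP*

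**What the plan says.** SAP, METHODS, states the co-primary hypotheses in these words: "BMI will decrease and quality of life will increase in the enhanced DPP arm relative to the standard DPP arm upon completion of the study". In the same paragraph it then defines the test. "To test whether the change in the primary outcome from baseline at 12 months differs between the standard and enhanced arms", the null hypothesis beta_6 = 0 is tested by a Wald test, at two-sided 0.05 for each outcome and 0.10 overall.

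The model has three post-baseline indicators, showing whether an observation "is at month 6, 12, or 18, respectively". Beta_6 is the intervention-by-month-12 term. Beta_7 is the intervention-by-month-18 term, and no test or role is stated for it.

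The protocol describes the length of the study in other ways:
- Section 2.g (Study Endpoint(s)): "We plan to continue the study for the full 20 months".
- Section 2.a (Procedures): "Questionnaires will be filled out at the clinic visits at baseline, 5 months, 8 months, 14 months, and 20 months". Blood samples and physical measurements follow the same visits, and the last cohorts are to have fewer follow-up evaluations.
- Section 4.h (exclusion criteria): "Plans to move during the study period (9 months post-randomization".

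SAP, SAMPLE SIZE AND DATA INTERPRETATION, names no time point for the powered comparison. Its SD of 4.5% is the cited DPP trial's 6-month value. The same sentence gives 4.9% (SD 7.4%) "at the end of the trial (mean follow-up of 3.2 years").

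**The concern.** A hypothesis and its test should name the same time point. Here the hypothesis points to the end of the study and the test points to the middle of three modelled follow-up times. Someone following the SAP to the letter would test month 12 and then report on a hypothesis about study completion.

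Two things are at stake. The first is what a positive result means: a significant beta_6 supports an arm difference at 12 months and says nothing direct about the last follow-up. The second is that the hypothesis wording could be cited after the data are seen to argue that beta_7 was the intended primary contrast. The SAP already accepts an overall alpha of 0.10 across two outcomes, so any choice between time points would come on top of that.

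**Working it through.** **1. The time points side by side**

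| Source | Time point |
|---|---|
| SAP hypothesis | study completion, not defined in months |
| SAP primary test (beta_6) | month 12 |
| SAP model, last time (beta_7, no stated test) | month 18 |
| Protocol 2.g | 20 months |
| Protocol 2.a visits | 5, 8, 14, 20 months |
| Protocol 4.h study period | 9 months |

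Neither document says that 12 months is study completion. Month 12 is 18 − 12 = 6 months before the last model time and 20 − 12 = 8 months before the last protocol visit. Against the 9-month period it falls 3 months after the end.

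**2. Does relabelling the visits remove the mismatch?** Matching each model month to its nearest visit gives 6→5, 12→14, 18→20. Shifting every model month by two gives 6→8, 12→14, 18→20. Both put beta_6 at the 14-month visit and beta_7 at the 20-month visit, so the tested contrast is still not the last one. Reconciling the schedule is necessary but does not by itself align hypothesis and test.

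**3. Is 12 months simply the end of treatment?** No. The protocol gives the intervention as 16 weeks in one place and 20 weeks in another. At 4.345 weeks per month these are 16/4.345 = 3.7 and 20/4.345 = 4.6 months. Counting from baseline, month 12 falls about 7.4 to 8.3 months after the programme ends.

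**4. If either contrast were accepted as primary (conditional).** Both coefficients subtract the same baseline. Under the SAP's random-intercept model with complete data, each participant's two changes have variance 2σ² and covariance σ², so the estimates correlate at σ²/2σ² = 0.5. The chance that at least one is significant at two-sided 0.05 under the null is then 9.1% per outcome (8.3% at correlation 0.7, 7.0% at 0.9), against the planned 5%. This applies only if the named test is set aside.

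**5. The SAP's sample size, and why its time point matters.** Inputs from the SAP: difference 2.0 points, SD 4.5, two-sided alpha 0.05, power 80%, 20% missing.
- Effect size 2.0/4.5 = 0.444. The two-sample t-test solution is 80.44, rounded up to 81 per arm. Then 81/0.8 = 101.25, rounded up to 102. Both SAP figures reproduce.
- Power with 81 evaluable per arm (normal approximation) is Φ(2.0/(SD·√(2/81)) − 1.96).

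| SD | SD·√(2/81) | Power |
|---|---|---|
| 4.5 (cited, 6 months) | 0.707 | 0.81 |
| 5.5 (assumed) | 0.864 | 0.64 |
| 6.5 (assumed) | 1.021 | 0.50 |
| 7.4 (cited, end of trial) | 1.163 | 0.41 |

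The documents give no SD at 12 or 18 months, so this is a sensitivity range. The 7.4 comes from a mean follow-up of 3.2 years and is an outer value.

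**The case against.** The strongest reply is that the primary test is not ambiguous. The SAP names the coefficient, the time, the statistic and the level, and states no test of beta_7. Presenting beta_7 as the planned primary result would contradict that sentence. This stands: beta_6 is the operative test, and the 9.1% figure describes a departure from the SAP, not its planned error rate.

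A reader might infer that 12 months cannot be the end of the study however the documents are read. They do not support anything so absolute. One exclusion criterion puts the study period at 9 months, and late cohorts have fewer follow-ups, so for some participants month 12 may be at or beyond their last visit. What can be said is that 12 months is not the last time in the SAP's own model and agrees with none of the protocol's statements.

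A reader might also infer that the SAP claims a lasting effect and then fails to test it. The SAP makes no such claim, and a contrast 7 to 8 months after the programme ends does examine some persistence. What has no stated test is the effect at the last follow-up.

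Finally, a reader might scale the 2.0-point difference by the cited trial's decline from 6.9% to 4.9% and conclude that the arm difference would shrink by 29% by the end. That is not supported. The decline is in one arm's mean, from 6 months to a mean follow-up of 3.2 years, whereas the gap here is 6 to 8 months. Both arms here receive a DPP, so regain common to both would cancel. The documents give no fade in an arm difference.

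It might also be said that the end-of-study phrase refers to when the analysis is done. That is the less natural reading, because the phrase qualifies the changes in BMI and quality of life.

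**Conclusion.** The mismatch is real and sits within one paragraph of the SAP. The hypotheses concern study completion. The only stated primary test concerns month 12, which is 6 months before the last modelled time and 8 months before the protocol's last visit. A significant beta_6 would not establish the hypotheses as worded. The effect at the last follow-up can be estimated from beta_7 but has no stated test.

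The consequence is for what the trial may conclude; the sample size arithmetic is correct. How large any difference between the month-12 and last-follow-up effects would be cannot be derived from the documents. Power for a 2.0-point difference with 81 per arm does depend on the SD at the chosen time: about 0.81 at the cited 6-month SD and about 0.41 at the cited end-of-trial SD, with intermediate values resting on assumption. These figures ignore cohort correlation and the repeated measures, as the SAP's own calculation does. They also assume 81 evaluable per arm, which may be optimistic at the last visit because late cohorts are followed for less time.

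**What to change.** 1. Reconcile model months 6, 12 and 18 with the protocol visits at 5, 8, 14 and 20 months, and the 9-month study period with the 20-month plan, so that the tested time point is a visit that exists.
2. In SAP, METHODS, replace the end-of-study phrase in the hypotheses with the time point that beta_6 tests, and limit the primary conclusion to it.
3. State that beta_7 will be reported with its confidence interval as a secondary, exploratory estimate of the effect at the last follow-up. This fits the SAP's existing treatment of secondary analyses. Giving beta_7 a higher rank would be a design preference and is not needed to cure the mismatch.
4. In SAP, SAMPLE SIZE AND DATA INTERPRETATION, state which time point the calculation refers to and note that the SD of 4.5% is a 6-month value. If the time point is later, show power over a range of SDs, since the documents give no value for 12 months.

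Items 2 and 3 cost only wording. Item 1 needs a decision on the schedule, and item 4 needs an SD from elsewhere or a declared range. Nothing here requires a change in sample size or new data. The downside is that the primary claim no longer covers the end of follow-up.

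### The primary model tests month 12 with terms for months 6, 12 and 18, but the protocol schedules follow-up at 5, 8, 14 and 20 months, and the time point of the co-primary test is contradictory

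*SAP*

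**What the plan says.** **SAP, Methods.** The primary model has three visit indicators, which "indicate whether observation k from subject j is at month 6, 12, or 18, respectively", and three intervention-by-visit interactions. The operative test is a Wald test of β6, the Month 12 interaction: "To test whether the change in the primary outcome from baseline at 12 months differs between the standard and enhanced arms". The sentence that introduces the model puts the co-primary hypotheses (BMI and quality of life) elsewhere in time: "relative to the standard DPP arm upon completion of the study". On data use, "The primary analyses will follow the intent-to-treat principle and will use all available data".

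**Protocol, section 2a.** The schedule is given twice. Blood samples and measurements are taken "at all of the evaluation visits (baseline, 5 months, 8 months, 14 months, and 20 months"), and "Questionnaires will be filled out at the clinic visits at baseline, 5 months, 8 months, 14 months, and 20 months". The same paragraph also says: "Participants will complete 3 evaluations during the research study: baseline, 5 months (1 week following the conclusion of intervention"). It adds that the last cohorts will have fewer follow-up evaluations. Section 2g plans for the study to run its full 20 months.

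Neither document schedules a visit at month 6, 12 or 18, defines a visit window, or says which protocol visit belongs to which model term.

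**The concern.** β6 carries the confirmatory conclusion for both co-primary outcomes. For it to mean one thing, the reader must know which visit is Month 12 and what happens to every other record. The documents fix neither. Someone has to decide when the data are coded, and if that happens after results by arm are visible, the choice is unprotected.

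Two things depend on it. The first is the estimand: an effect at 14 months and one at study completion are different quantities unless the effect happens to be equal at those two visits. Because the last cohorts have fewer follow-ups, the choice also changes who contributes data. The second is the estimate: with four follow-up visits and three terms, the surplus visit can be merged, dropped, given its own term or left in the baseline reference, and these options do not all estimate the same thing.

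**Working it through.** **1. The plan's own figure.** The sample size reproduces. 2.0/4.5 = 0.444; a two-sided t-test at 0.05 with 80% power needs 80.44, so 81 per arm; 81/0.80 = 101.25, so 102. This is a simple two-group comparison that does not use the visit schedule, so the point below does not alter it.

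**2. Months side by side.** Scheduled: {5, 8, 14, 20}. Modelled: {6, 12, 18}. The intersection is empty. Taken literally, all six visit and interaction columns are zero for every scheduled record. Only the intercept, arm and gender remain (rank 3 of 9), and β6 cannot be estimated.

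**3. Two plausible mappings, neither stated.**

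| Scheduled visit | Nearest modelled month (gap) | Constant two-month shift |
|---|---|---|
| 5 | Month 6 (1) | no term |
| 8 | Month 6 (2) | Month 6 |
| 14 | Month 12 (2) | Month 12 |
| 20 | Month 18 (2) | Month 18 |

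Both make the model estimable (rank 9 of 9) and both put β6 at 14 months. They differ on the 5-month visit, the one just after the intervention ends.

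**4. Which time point.** The Wald test says 12 months, the mappings suggest 14, and the hypothesis sentence says study completion, which is 20 months in protocol 2g. The exclusion criterion on moving away gives yet another length, a study period of 9 months after randomisation, which contains only the 5- and 8-month visits.

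**5. What the handling of the 5-month visit does to β6.** Assumptions: participant random-intercept model (cohort intercept and gender omitted), equal arms, between-participant SD 3, 6 or 12, and a true 14-month difference d14 = -2.0. That is the SAP's planning difference in percentage points of weight; the proportions do not depend on the unit. Let d5 be the effect at 5 months.

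- *Own term, complete follow-up:* β6 = d14 = -2.0.
- *Merged with 8 months, complete follow-up:* β6 = -2.0. If 10-30% have only baseline and 5 months, and the 5- and 8-month effects differ by 1.0 (all assumed), β6 shifts by 0.02 to 0.08, which is immaterial.
- *Left in the reference, complete follow-up:* the reference is the mean of baseline and 5 months, so β6 = d14 - (0 + d5)/2. For d5 = 0, -1.0, -2.0 this gives -2.0, -1.5, -1.0.
- *Excluded:* β6 = -2.0 if dropout is unrelated to the 5-month result. If it is related, β6 can be biased. Simulations with a true effect of -2.0 at every follow-up visit, and dropout after 5 months made to depend on the change at 5 months, gave about -1.87 to -1.96 when the dependence held in both arms. They gave about -1.48 to -1.84 when it held only in the standard arm. In the same setting, an own term or merging recovered about -2.0. The dropout rules are assumed; the documents give none.

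**6. What cannot be computed.** Power at 8, 14 or 20 months cannot be stated. The SAP gives an SD only at 6 months (4.5) and at a mean of 3.2 years (7.4), both for percent weight change while the modelled outcome is BMI, and none for quality of life.

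**The case against.** The strongest reply is that months 6, 12 and 18 are loose labels, perhaps counted from a different origin, which would produce exactly a constant two-month shift. An analyst would then put Month 12 at 14 months under either obvious rule, and the SAP's wording about change from baseline argues against leaving a follow-up record in the reference. Much of this stands: 14 months is the most natural reading, and the damaging option is the least likely one. But no sentence states the origin or the mapping, the 5-month visit remains unassigned, and labelling does not explain why the hypothesis sentence points to study completion.

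Stronger readings are tempting, and the documents do not support them:

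- *That one scheduled visit has no term.* This holds under the two-month shift only. Under nearest-month matching all four visits have a term, and literally none has.
- *That the SAP's change list proves the schedule was unchanged.* It has two items, a change of site and "Blood samples were obtained by fingerstick method rather blood draw", and neither concerns visits. But it lists changes from an original protocol. The protocol at hand already names the new site, so it is not shown to be that original.
- *That the protocol is right and the SAP wrong.* The protocol's count of three evaluations conflicts with its own list of baseline plus four.

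**Conclusion.** The point holds. The co-primary test is set at a month with no scheduled visit, four follow-up visits face three terms with no stated mapping, and the hypothesis sentence and the test name different times. It should be settled before the arms are compared, because it concerns the confirmatory test itself.

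A reader might infer that β6 is biased, or that the analysis is bound to fail. The documents show neither. The model cannot be estimated only if the month labels are taken literally. The halving from -2.0 to -1.0 requires both that the 5-month visit is coded into the reference and that its effect is already -2.0. The bias from exclusion requires dropout that depends on the 5-month result. What is established is an open choice with a possible effect on β6 ranging from none to a halving under the stated assumptions, and an unresolved time point.

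**What to change.** 1. Establish which visits were actually held and reconcile the protocol and SAP to them, including the three evaluations against baseline plus four.
2. Give each follow-up visit its own indicator and intervention-by-visit term, with visit windows, so that only baseline records form the reference.
3. Name one visit as the primary time point and use it identically in the hypothesis sentence, the Wald test and the protocol. State how many participants are expected to reach it, given the shorter follow-up of the last cohorts.
4. If data are already collected, which the SAP's past tense about blood sampling suggests, make the change in a dated SAP amendment before the arms are compared.

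Cost: text and a visit-window table. If all four visits stand, there is one more indicator and one more interaction (11 fixed effects instead of 9, full rank). The calculated sample size does not change. The real cost may lie in a late primary visit: 102 - 81 = 21 participants per arm (21/102 = 20.6%) can be missing before an arm falls below the planned 81, and missingness at 14 or 20 months may exceed the 20% allowed for.

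### The primary model estimates a baseline arm difference that randomisation already sets to zero, so the month-12 test is valid but less precise than the same data allow

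*SAP*

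**What the plan says.** The primary model (SAP, METHODS) has an Intervention main effect, indicators for months 6, 12 and 18, and an interaction of Intervention with each of the three. Baseline is the reference visit, so β1 is the arm difference at baseline and is left free. The model has a random cohort intercept and "a random intercept β_{0ij} to account for within participant correlation". It "adjusts for gender" and contains no baseline-outcome covariate.

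The aim of the Wald test of β6 = 0 is given as "To test whether the change in the primary outcome from baseline at 12 months differs between the standard and enhanced arms". BMI and quality of life are co-primary and share this model: "Each outcome will be tested at a two-sided" α of 0.05. Secondary outcomes are put through the same model.

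The protocol (section 2.a, Procedures) fixes the order of events: "After all baseline data is collected, the participant is randomly assigned to ONE of two groups".

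The sample size section of the SAP works from weight alone: "Dividing a 2.0% difference (6.0%-4.0%) by the DPP SD (4.5%) yields an effect size of approximately 0.45". It gives no SD, correlation, target effect or power for quality of life.

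**The concern.** Because baseline is measured before allocation, any arm difference there is chance. A model that estimates it freely subtracts the whole of that chance difference from the month-12 difference. In effect, baseline gets a weight of one. The efficient weight under a random-intercept model is ρ, and the gap between one and ρ is added noise.

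What is at stake is precision, outcome by outcome. Where visits are very highly correlated, as for BMI, a weight of one is close to ideal. For a questionnaire score with moderate correlation it is not, and below ρ = 0.5 the change score is less precise than comparing month-12 values alone. Quality of life is tested at its own α, yet the plan documents no power for it. An avoidable loss is therefore most likely to matter there.

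**Working it through.** **1. The plan's own figure.** 2.0/4.5 = 0.444. A two-sample t-test at two-sided α 0.05 and 80% power needs 80.44, so 81 per arm (power at 81: 80.3%). Allowing for 20% missing, 81/0.8 = 101.25, so 102. Both stated figures reproduce. The SD used is described as "the standard deviation of weight change in past clinical trials of lifestyle interventions", so this calculation is already on the change-score scale.

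**2. Variance with complete data.** Let σ² be the variance at one visit, n the number per arm, and ρ the baseline to month-12 correlation within a participant.

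- β1 free (as planned): β6 is the arm difference in mean change, with variance (2/n) × 2σ²(1−ρ).
- β1 = 0: the estimate is the month-12 difference minus ρ times the baseline difference, with variance (2/n) × σ²(1−ρ²).
- Ratio: (1−ρ²) / [2(1−ρ)] = (1+ρ)/2.

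Mixed-model fits to three simulated complete data sets agreed: β6 equalled the raw difference in mean change each time (0.4735, 0.2560, 0.1689).

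**3. Variance with about 20% missing.** The generalised least squares variance was computed for three missingness patterns, using all available visits. β6 is then no longer exactly the completers' change difference (0.337 against 0.351 in one simulated set). Its variance is up to about 8% below that of the change score for ρ of 0.4 to 0.8, but most of the loss remains. The calculation uses the participant intercept and leaves out the cohort intercept, so ρ should be read as the correlation within cohort.

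**4. Quality of life.** Assumed inputs, not in the documents: ρ from 0.4 to 0.8 and a true effect of 0.35 SD. Completers per arm: 102 × 0.8 = 81.6. Power is from the noncentral t, with standardised effect 0.35/√[2(1−ρ)] as planned and 0.35/√(1−ρ²) with β1 = 0. At ρ = 0.5 these are 0.35/1 = 0.350 and 0.35/√0.75 = 0.404.

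| Assumed ρ | Variance ratio, complete data | Variance ratio, about 20% missing | Power as planned | Power with β1 = 0 |
|---|---|---|---|---|
| 0.4 | 0.70 | 0.74 to 0.75 | 53% | 68% |
| 0.5 | 0.75 | 0.79 | 60% | 73% |
| 0.6 | 0.80 | 0.83 | 70% | 79% |
| 0.7 | 0.85 | 0.87 to 0.88 | 82% | 88% |
| 0.8 | 0.90 | 0.91 to 0.92 | 94% | 96% |

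The power columns use completers only and the complete-data ratio, so they slightly overstate the gain when partial data are also used.

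**5. BMI.** With height fixed, percent weight change equals percent BMI change. The SAP's 4.5% change SD then implies ρ = 1 − (0.045 × mean BMI)² / (2 × SD²). Mean and SD of baseline BMI are assumed at 35 to 40 and 5 to 7.

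- Mean 37, SD 6: 1 − 1.665²/72 = 0.961; ratio 0.981.
- Extremes: mean 40, SD 5 gives ρ 0.935; mean 35, SD 7 gives 0.975. The saving is about 1% to 3%.
- With the 7.4% SD that the SAP also quotes, ρ is about 0.83 to 0.93 and the saving about 3% to 9%.

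At ρ = 0.954 and 81 per arm, power for weight would move from 80.3% to 81.2%.

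**The case against.** The strongest reply is that nothing here is an error. The SAP names its target, the arm difference in change at 12 months, and the model tests that target. A mixed model with free group-by-visit terms is a standard choice, and β6 is unbiased with correct size under it. This stands: the point concerns efficiency only.

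The second reply is that the one outcome with a documented sample size hardly gains. That also stands. A reader might infer that the stated 80% power is too optimistic, but the SD behind it is an SD of change, so the calculation already matches a change-score test.

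The third is that the quality-of-life figures rest on assumption. This is correct, and it is why a range is shown: the power gain runs from about 15 points at ρ = 0.4 to about 2 at ρ = 0.8. A reader might conclude that quality of life is underpowered, or that it certainly bears most of the loss. The documents support neither statement, because they give no correlation, SD or effect for it. The direction needs no such input, since (1+ρ)/2 is below 1 for every ρ below 1.

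A reader might also infer that baseline values are thrown away. They are not. They enter with a weight of one, and what goes unused is the equality of arms that randomisation provides.

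**Conclusion.** The point holds as a matter of avoidable imprecision, not of validity. Its structure rests on the documents alone: β1 is free, no term adjusts for the baseline outcome, and allocation follows baseline. The complete-data ratio (1+ρ)/2 follows from the random-intercept model.

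The size depends on ρ. For quality of life the variance saving is 30% to 10% with complete data, and about 26% to 8% with about 20% missing, if ρ lies between 0.4 and 0.8. For BMI it is about 1% to 3% under the assumed baseline spread and the 4.5% SD. That the gain falls mainly on quality of life is plausible, but it requires that outcome's ρ to be clearly below that of BMI. The change is worth making because it uses data already planned; leaving the model as it is would not invalidate the trial's result.

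**What to change.** Before outcomes are examined by arm, remove the Intervention main effect from the SAP equation so that both arms share one baseline mean, and keep the three Intervention-by-month terms. β6 still targets the same quantity, because with equal baseline means the arm difference in change is the arm difference at month 12. Cite the protocol's order of baseline and randomisation as the justification.

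A similar alternative is to model only the follow-up visits with the baseline outcome as a covariate. It is not identical: it drops participants with no follow-up and estimates the baseline slope freely.

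State an assumed correlation, SD and target effect for quality of life, so that its precision can be judged.

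The cost is one model term and a dated, justified amendment; no new data, visits or participants are needed. Timing matters: the SAP is dated October 2019 and describes blood sampling in the past tense, so data collection was probably under way. If outcomes by arm have already been seen, keep the planned model as primary and report the constrained one as a labelled sensitivity analysis.
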